## 8.0 GUIDELINES FOR ADVERSE EVENT REPORTING

### 8.1 Adverse Event Reporting/Institutional Policy

The following guidelines are the minimum Cancer Consortium IRB adverse event (AE) reporting guidelines. Protocol-specific additional reporting requirements for adverse events are addressed in Section 8.2.

In accordance with institutional policy, all adverse events which in the opinion of the PI are unexpected and related or possibly related to the research and serious or suggest that the research places research participants or others at greater risk of physical or psychological harm than was previously known or recognized be reported to the IRB within 10 calendar days of learning of the problem.

#### Definitions:

**Adverse Event (AE)** - Any untoward medical occurrence in a patient or clinical investigation subject administered a pharmaceutical product, medical treatment or procedure and which does not necessarily have to have a causal relationship with this treatment. An adverse event can therefore be any unfavorable and unintended sign (including

an abnormal laboratory finding, for example), symptom, or disease temporally associated with the use of a medicinal product, medical treatment or procedure whether or not considered related to the medicinal product.

**Life-threatening AE** – Any adverse event that places the patient or subject, in view of the investigator, at immediate risk of death from the reaction.

**Unexpected AE** – An adverse event is “unexpected” when its nature (specificity), severity, or frequency are not consistent with (a) the known or foreseeable risk of adverse events associated with the research procedures described in the Protocol-related documents, such as the IRB-approved research protocol, informed consent document and other relevant sources of information such as product labeling and package inserts; and are also not consistent with (b) the characteristics of the subject population being studied including the expected natural progression of any underlying disease, disorder or condition any predisposing risk factor profile for the adverse event.

**Attribution** - The following are definitions for determining whether an adverse event is related to a medical product, treatment or procedure:

- An adverse event is “**related or possibly related to the research procedures**” if in the opinion of the PI, it was more likely than not caused by the research procedures.
- Adverse events that are solely caused by an underlying disease, disorder or condition of the subject or by other circumstances unrelated to either the research or any underlying disease, disorder or condition of the subject are not “related or possibly related.”
- If there is any question whether or not an adverse event is related or possibly related, the adverse event should be reported.

The Cancer Consortium Expedited Reporting Form should be completed for all adverse events that meet the expedited reporting requirements. The AE form (see **Appendix I**) should be faxed to the FHCRC Research Coordinator at [contact] within 10 business days of study staff awareness. All available information should be submitted.

### **8.2 Study-Specific AE Capture**

Please refer to the package insert of deferasirox for a listing of specific expected AEs.

AEs will be reviewed and captured in the source documentation. AEs occurring from enrollment through 30 days after the last administration of the study treatment will be captured in protocol-specific case report forms (**Appendix J**).

The following events are not recorded as AEs in this study:

- Disease progression or relapse.
- Planned medical or surgical procedures in and of themselves, including those that require hospitalization (e.g., surgery, endoscopy, biopsy procedures) are not considered AEs.
- Abnormal laboratory values grade < 3 (CTCAE v4.03).

In accordance with institutional policy, all SAEs which in the opinion of the PI or designee meet all three of the following criteria will be reported to the IRB within 10 calendar days of learning of the problem:

1. unexpected
2. related or possibly related to the research
3. serious or suggests that the research places research participants or others at greater risk of physical or psychological harm than was previously known or recognized

All other SAEs and deaths, not meeting the expedited reporting criteria, will be reported to the IRB as part of the annual continuation review report to the IRB.

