Based on preclinical and clinical data, mechanisms underlying the inferior survival in this population point to excess in labile plasma iron (LPI) as the putative mediator(19). This has prompted the use of ICT to modify the negative effect of iron overload in patients with MDS. Although several reports suggest a survival benefit with ICT (27-31), all of them were non-randomized comparisons and were susceptible to a significant selection bias. We know that patients are selected to receive ICT on the basis of an expected survival; otherwise, they would not live long enough to benefit. Therefore, the improved survival in patients treated with ICT could be completely due to a selection bias that is not necessarily overcome by a matched pair

In a multicenter, open-label, single-arm, 3-year phase II trial (US03), the safety and tolerability of deferasirox was evaluated in lower-risk MDS who had received at least 20 units of RBC and had a serum ferritin  $\geq 1,000 \mu\text{g/L}$ (34). Of the 173 patients that underwent ICT with deferasirox, 51 (28%) experienced hematologic improvement, only seven of which received other MDS related therapy. Therefore, ICT appears to improve hematologic parameters in some MDS patients with iron overload. Mean labile plasma iron (LPI) was measured at baseline in 163 patients, among these patients 68 had elevated levels ( $>0.5 \text{ LPI units}$ ). Concentrations of LPI fell within normal limits in all 47 patients who were assessed at week 13 and remained in the normal range through the duration of the trial (Figure 3). Additionally, there was a decline in the median serum ferritin by 23.2% at one year in the patients who completed at least one year of ICT. Therefore, deferasirox was able to reduce the iron burden in iron-overloaded MDS patients.

[figure not shown]

Figure 3: Mean LPI over 12 months in MDS patients with abnormal LPI at baseline.

The annual discontinuation rates of deferasirox were 45%, 43%, and 35% during years 1, 2, and 3 respectively. The safety profile of deferasirox in this setting was reasonable with discontinuation in 43 patients (24.8%) because of adverse events (such as gastrointestinal disturbances) or disease progression and 23 patients (13.2%) because of abnormal laboratory values (such as increased serum creatinine). All 28 deaths that occurred during the study were considered unrelated to deferasirox.

[figure not shown]

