### **2.3 Study Agent**

Patients will receive oral deferasirox which has been approved by the FDA for the treatment of chronic iron overload due to blood transfusions in patients 2 years of age or older. Deferasirox will be administered to achieve a ferritin < 100 ng/mL and, since it is approved for chelation and used regularly for this purpose as a standard of care, the dosing and schedule will be at the discretion of the treating clinician based on overall iron loading (ferritin), renal function, hepatic function, blood counts, and clinical condition / performance status. Contraindications include the following: Serum creatinine greater than two-times the upper limit of normal (ULN) or glomerular filtration rate (GFR) of less than 40 mL/min, poor performance status, high risk MDS, advanced malignancies, platelet count of less than 50,000, pregnancy, and/or known hypersensitivity to deferasirox.

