### **2.4 Risks/Benefits**

The most frequently occurring adverse reactions are diarrhea, vomiting, nausea, abdominal pain, skin rashes and increases in serum creatinine. Among patients with MDS, the major observed toxicity was an increase in serum creatinine (37%). The most frequent adverse reactions that led to drug discontinuation were increase in serum creatinine, diarrhea, nausea, rash and vomiting. Death was reported in the first year in 8% of the patients. Auditory and ocular disturbances occurred in <1% of participants. Deferasirox is considered pregnancy Category C by the FDA as animal studies have demonstrated potential embryonal fetal toxicities with decreased offspring viability with renal anomalies. The potential benefits of deferasirox are reduction in total body iron with improvement in organ function (liver and heart). Additional benefits include the potential to improve hematopoiesis and bone marrow function in general.

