#### 4.2.2 Secondary Endpoints

1. Change in RBC transfusion requirements.
2. The proportion of patients who achieve granulocyte or platelet hematologic improvement as defined by the modified IWG response criteria(39).
3. Change in serum ferritin levels from baseline to the end of the study as measured on a monthly basis.
4. Safety and tolerability profile as measured by grade 3 and 4 non-hematologic adverse events

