### 7.6.3 Renal Impairment

Serum creatinine and proteinuria should be monitored during the study as stated in Table 2.

Deferasirox can cause acute renal failure, fatal in some patients and requiring dialysis in others. Postmarketing experience showed that most fatalities occurred in patients with multiple comorbidities and who were in advanced stages of their hematological disorders. In the clinical trials, deferasirox-treated patients experienced dose-dependent increases in serum creatinine.

Measure serum creatinine and determine the glomerular filtration rate (GFR, estimated by the MDRD method) before initiating therapy in all patients.

Deferasirox is contraindicated in patients with an estimated GFR less than 40 mL/minute or serum creatinine greater than 2 times the age-appropriate upper-limit-of-normal (ULN). Renal tubular damage, including Fanconi's Syndrome, has been reported in patients treated with deferasirox, most commonly in children and adolescents with beta-thalassemia and serum ferritin levels <1500 mcg/L.

Deferasirox will be administered and dosed at the discretion of the treating clinician based on renal function as measured by serum creatinine and via the estimated GFR.

Intermittent proteinuria of unclear significance was also noted in clinical trials with deferasirox. The level of proteinuria will be measured per Table 2 (at baseline before treatment, at 6 months and again at 12 months) strictly for monitoring. Deferasirox will be administered and dosed at the discretion of the treating clinician based on the

results of monitoring for proteinuria. However, given the intermittent nature of proteinuria experienced with deferasirox and its unclear significance, there is no contraindication to the administration of deferasirox based on level of proteinuria.

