### 9.4.1 AE Grading

Toxicities will be graded using the NCI Common Terminology Criteria for Adverse Events (CTCAE) Version 4.03. Citing the website under this section in the protocol rather than printing the entire document is sufficient unless the study is modifying the criteria. The scale in its entirety can be found at:

[http://evs.nci.nih.gov/ftp1/CTCAE/CTCAE\\_4.03\\_2010-06-14\\_QuickReference\\_8.5x11.pdf](http://evs.nci.nih.gov/ftp1/CTCAE/CTCAE_4.03_2010-06-14_QuickReference_8.5x11.pdf)

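### The safety and tolerability endpoint counts only grade 3–4 non-hematologic AEs, so a patient who stops or reduces deferasirox for a lower-grade laboratory change goes uncounted

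*Combined protocol and SAP*

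**What the plan says.** - **Endpoint.** Section 4.2.2 item 4 reads: "Safety and tolerability profile as measured by grade 3 and 4 non-hematologic adverse events". No other endpoint, and nothing in Sections 12.3 or 15.0, counts discontinuations, interruptions or dose reductions.
- **AE recording.** The definitions in Section 8.1 allow an abnormal laboratory finding to be an AE. Section 8.2 then lists what is not recorded, including "Abnormal laboratory values grade < 3 (CTCAE v4.03". It makes no exception for relatedness, dose change or stopping.
- **Grading.** Section 9.4.1: "Toxicities will be graded using the NCI Common Terminology Criteria for Adverse Events (CTCAE) Version 4.03". The scale is cited by web address; its cut-offs are not printed.
- **Treatment decisions.** Section 7.6.3 leaves renal dosing to the treating clinician. Section 7.7 leaves removal for safety to the PI or designee. Neither is tied to a grade.
- **Renal limits.** Section 7.6.3: "Deferasirox is contraindicated in patients with an estimated GFR less than 40 mL/minute or serum creatinine greater than 2 times" the upper limit of normal (ULN). Section 2.3 gives the same limits.
- **Expected toxicity.** Section 2.4: "Among patients with MDS, the major observed toxicity was an increase in serum creatinine (37" percent). The same section puts raised creatinine first among reactions leading to discontinuation. For the earlier 3-year phase II trial, Section 2.2 reports that deferasirox was stopped in "23 patients (13.2%) because of abnormal laboratory values (such as increased serum creatinine").

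**The concern.** An endpoint labelled tolerability would be expected to register patients who cannot stay on the drug. This one does so only if the event behind the stop reaches grade 3. For laboratory changes the gap is double: below grade 3 they are neither endpoint events nor AE records.

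The toxicity affected is the one the protocol's own background makes most likely, in a trial that treats to a ferritin below 100 ng/mL and says there is little clinical experience with chelation when ferritin is below 1000 ng/mL (Section 2.2). The risk is a report of good tolerability that is silent about patients whose treatment was reduced or ended for renal or other laboratory values. There is no toxicity stopping rule (Section 16.0), so the descriptive safety summary carries much of the safety message. The primary endpoint is not affected.

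**Working it through.** **Step 1: follow one patient through the rules.** Suppose creatinine rises to a level below grade 3 and the clinician stops deferasirox.

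1. Sections 7.6.3 and 7.7 permit the stop on judgment, whatever the grade.
2. Section 8.2: the value is not recorded as an AE.
3. Section 4.2.2 item 4: no grade 3–4 event, so nothing is counted.
4. Sections 9.1 and 9.2: it is reported only if it meets a seriousness criterion, which an outpatient laboratory change need not do.

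No grade cut-off is needed for this step. It holds for any laboratory change below grade 3 that leads to a treatment change.

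**Step 2: which section decides.** Delete the 8.2 exclusion and repeat. The patient now has an AE record, but item 4 still admits only grades 3 and 4, so the endpoint is unchanged. Section 4.2.2 is therefore the deciding cause; 8.2 removes the record that would otherwise show the event.

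**Step 3: scale.** Inputs: 23 of 173 stops for laboratory values (Section 2.2), 37% with raised creatinine (Section 2.4), and 25 patients (Section 15.0).

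- Plan's own figure: 23/173 = 13.29%, stated as 13.2%. These agree apart from rounding.
- Expected laboratory-driven stops: 25 × 0.1329 = 3.3.
- Expected creatinine rises of any grade: 25 × 0.37 = 9.25.

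The documents do not say what share *s* of such stops is below grade 3. Uncounted stops = 25 × 0.1329 × *s*. The chance of at least one, treating patients as independent, is 1 − (1 − 0.1329 × *s*)^25.

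| Share below grade 3 (assumed) | Expected uncounted stops | Chance of at least one |
|---|---|---|
| 0% | 0 | 0 |
| 25% | 0.8 | 0.57 |
| 50% | 1.7 | 0.82 |
| 75% | 2.5 | 0.93 |
| 100% | 3.3 | 0.97 |

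The 13.2% covers all laboratory reasons over 3 years. Treatment here lasts at most one year (Section 7.4), so these counts are probably too high.

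**Step 4: the protocol's renal limits.** Let grade 3 begin above *c* × ULN, with *c* an assumption.

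- A creatinine past the 2 × ULN limit stays below grade 3 only between 2 and *c*. With *c* = 2 there is no gap; with *c* = 2.5 it is 2 to 2.5; with *c* = 3 it is 2 to 3.
- If the scale also grades against the patient's own baseline, the gap narrows. Suppose grade 3 also begins above 3 × baseline. Then 2.5 × ULN is already grade 3 when baseline is below 2.5/3 = 0.83 × ULN, and 2 × ULN when baseline is below 2/3 = 0.67 × ULN. Entry allows creatinine up to 1.5 × ULN (Section 5.1), so patients on both sides of these values are eligible.
- A GFR below 40 stays below grade 3 only if the grade 3 limit is itself below 40.

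The documents fix none of these cut-offs.

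**The case against.** The strongest reply is that nothing is hidden. Creatinine, GFR and liver tests are scheduled every two weeks in the first month and monthly thereafter (Section 7.3, Table 2, Appendix F). Every serious event is reported whatever its grade (Section 9.2). The PI or designee reviews each patient's course weekly, and a DSMB reviews toxicity every six months (Sections 10.0 and 16.0). The 8.2 exclusion is consistent with an endpoint restricted to grades 3–4, and this is a descriptive secondary endpoint.

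Much of this stands. These values are unrecorded as AEs, not lost, and could be tabulated at any time. What remains is that nothing commits anyone to tabulate them or to count treatment changes.

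Four stronger readings are tempting but not supported:

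- *The 8.2 rule alone causes the gap.* It does not; see Step 2.
- *Values past the contraindication limits escape the endpoint.* This depends on cut-offs that are not printed and, for creatinine, possibly on baseline. The limits are also stated as contraindications, not as on-treatment stopping rules.
- *The DSMB shares the blind spot.* Sections 10.0 and 16.0 do not confine its toxicity data to AE entries. The case report form (Appendix J) is not in the available text, so reasons for stopping may be captured there.
- *There is a 97% chance of an uncounted stop.* That is the chance of any laboratory-driven stop at the earlier trial's rate; it applies to uncounted stops only if all of them are below grade 3. Likewise, the 37% has no grade attached, so it does not show how many patients would pass a renal limit.

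**Conclusion.** The point holds in this form: the safety and tolerability endpoint cannot register a treatment change made for a laboratory value below grade 3, and Section 8.2 means there is no AE record to recover it from. That follows from the protocol's text alone.

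The size is uncertain: between 0 and 3.3 of 25 patients at the earlier trial's rate, probably fewer over one year. This assumes that the earlier trial's rate carries over to these patients, and the grade split is unknown. The effect is confined to the safety and tolerability report. The change is still worth making, because the endpoint is least sensitive to the toxicity the protocol itself puts first, and the remedy is cheap.

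**What to change.** 1. **Section 4.2.2 item 4.** Add the number of patients who discontinue, interrupt or reduce deferasirox for an AE or a laboratory value, with reasons. Add a table of scheduled on-treatment creatinine and GFR against the limits already stated in Sections 2.3 and 7.6.3. These serve as reporting thresholds only, not as stopping rules.
2. **Section 8.2.** Except from the exclusion of laboratory values below grade 3 any value that leads to dose reduction, interruption or discontinuation.

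Both changes are needed: the second alone would create AE records that the endpoint still ignores.

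The cost is a few more AE entries and one extra table. The renal table needs no new tests. Counting dose changes with reasons may need one case report form field, since neither Table 2 nor the Appendix F calendar lists them. The reported safety profile may look slightly less favourable.

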## **9.0 Serious Adverse Events**

### **9.1 Definitions**

Serious adverse event (SAE) is defined as one of the following:

- Is fatal or life-threatening
- Results in persistent or significant disability/incapacity
- Constitutes a congenital anomaly/birth defect
- Is medically significant, i.e., defined as an event that jeopardizes the patient or may require medical or surgical intervention to prevent one of the outcomes listed above
- Requires inpatient hospitalization or prolongation of existing hospitalization,
- Note that hospitalizations for the following reasons should not be reported as serious adverse events:
  - Routine treatment or monitoring of the studied indication, not associated with any deterioration in condition
  - Elective or pre-planned treatment for a pre-existing condition that is unrelated to the indication under study and has not worsened since signing the informed consent
  - Social reasons and respite care in the absence of any deterioration in the patient's general condition
- Note that treatment on an emergency outpatient basis that does not result in hospital admission and involves an event not fulfilling any of the definitions of a SAE given above is not a serious adverse event

## 9.2 Reporting

To ensure patient safety, every SAE, regardless of suspected causality, occurring after the patient has provided informed consent and until at least 30 days after the patient has stopped study treatment must be reported to the study PI and/or study coordinator within 24 hours of learning of its occurrence.

Any SAEs experienced after this 30 days period should only be reported to the study PI and/or study coordinator if the investigator suspects a causal relationship to the study treatment. Recurrent episodes, complications, or progression of the initial SAE must be reported as follow-up to the original episode within 24 hours of the investigator receiving the follow-up information. An SAE occurring at a different time interval or otherwise considered completely unrelated to a previously reported one should be reported separately as a new event.

Information about all SAEs is collected and recorded on the Serious Adverse Event Report Form; all applicable sections of the form must be completed in order to provide a clinically thorough report. The investigator must assess and record the relationship of each SAE to each specific study treatment (if there is more than one study treatment), complete the SAE Report Form in English, and send the completed, signed form by [contact]) () within 24 hours to the study PI and study coordinator..

Follow-up information is sent to the same contact(s) to whom the original SAE Report Form was sent, using a new SAE Report Form stating that this is a follow-up to the previously reported SAE and giving the date of the original report. Each re-occurrence, complication, or progression of the original event should be reported as a follow-up to that event regardless of when it occurs. The follow-up information should describe whether the event has resolved or continues, if and how it was treated, whether the blind was broken or not, and whether the patient continued or withdrew from study participation.

## 9.3 Pregnancies

To ensure patient safety, each pregnancy occurring while the patient is on study treatment must be reported to the study PI and/or study coordinator within 24 hours of learning of its occurrence. The pregnancy should be followed up to determine outcome, including spontaneous or voluntary termination, details of the birth, and the presence or absence of any birth defects, congenital abnormalities, or maternal and/or newborn complications.

